## **Study Protocol**

### **Objectives:**

The objective of this research study is to examine the efficacy and behavioral and neural mechanisms of a cognitive emotion regulation training intervention aimed at improving psychological outcomes such as reducing depressive symptoms and grief rumination in bereaved spouses. Training efficacy will be assessed through psychological and neural indices of negative affect, and physiological indices including respiratory sinus arrhythmia (RSA), a measure of heart-rate variability. Cognitive reappraisal (i.e. the ability to modify the trajectory of an emotional response by thinking about and appraising emotional information in an alternative, more adaptive way) represents a highly promising target for psychological intervention in bereavement. Reappraisal can be operationalized via two primary tactics: psychological distancing (i.e. appraising an emotional stimulus as an objective, impartial observer) and reinterpretation (i.e. imagining a better outcome than what initially seemed apparent). The project builds upon promising preliminary work to investigate the effectiveness and underlying neurobiological mechanisms of a novel, five-session cognitive reappraisal intervention in bereaved spouses. The study aims to mechanistically relate changes in psychological, psychophysiological, and neural function during a novel emotion regulation intervention never before implemented in this stressed, high risk group. The goal is to inform future interventions that can reduce negative psychological outcomes in bereaved spouses.

### **Design:**

Recently-bereaved participants (i.e. approximately 6 months post-spousal loss) will be screened for eligibility, then randomly assigned to receive training in either distancing or reinterpretation, with five sessions occurring every 1-3 days, with longitudinal collection of affective, psychophysiological, and functional magnetic resonance imaging (fMRI) data. During the five sessions (T1-T5), participants will undergo cognitive emotion regulation training and an emotion regulation task in their respective training groups, complete questionnaires, and take a 5 minute RSA reading. Functional MRI scans will be acquired at T1 and T5. Follow-up questionnaire assessments of perceived stress, depressive symptoms and grief rumination will occur at one and two months post-intervention. We propose to recruit 84 participants in this study (i.e., 42 participants per intervention cell).

## Methods:

**Reappraisal Intervention Procedure.** At sessions T1-T5, participants will complete a widely used image-based reappraisal task. In the task, participants view non-violent images from the IAPS with themes relevant to grief and loss in bereavement. Task images are distinct from training images but contain the same themes. Neutral images contain at least one person but are emotionally neutral. All images at every session will be unique, presented in a randomized order, and counterbalanced across sessions and negative trial types. In the task, images are preceded by a cue word (either “LOOK” or “DECREASE”). On LOOK trials, participants will be asked to look at the image to-follow and respond naturally to it. On DECREASE trials, participants will be instructed to apply the appropriate regulation strategy (i.e., either distancing or reinterpretation) to decrease their emotional response to the image. Participants trained in distancing will be asked to alter the way they think about a personal connection to situations by viewing the photos with a rational, impartial mindset or imaging the events happened a long time ago, whereas participants trained in reinterpretation will be asked to tell themselves a story about the photos that whatever is going on will soon be better than it is now or the pain the person is feeling will be easier to bear with time. The resulting three trial types are: LOOK paired with a neutral image (“Look Neutral”), LOOK paired with a negative image (“Look Negative”), and DECREASE paired with a negative image (“Reappraise Negative”). One hundred and eighty total negative and 90 total neutral images are used in the task, with 18 trials per trial type per session, distributed evenly among 3 task runs. Following the presentation of each image, participants will be asked to rate their negative affect on a scale of 1 (least negative) to 4 (most negative).

**Self-report Questionnaires.** Negative affect ratings will be assessed at T1 through T5. Perceived stress will be assessed using the Perceived Stress Scale (PSS) at T1 through T5 and both follow-ups. Participants will complete additional self-report questionnaires at T1, T5, and both follow-ups measuring depressive symptoms using the Center for Epidemiologic Studies Scale (CES-D), intensity and nature of grief-related cognitive processes using the Utrecht Grief Rumination Scale (UGRS), and emotion regulation strategy use using the Emotion Regulation Questionnaire (ERQ).

**Functional Magnetic Resonance Imaging.** Participants will complete the picture task at sessions T1 and T5, while undergoing functional magnetic resonance imaging (fMRI) using a simultaneous multislice (SMS)-accelerated (3x) EPI acquisition protocol (63 axial slices; TR=1.2 s; TE=27 ms, 2-mm cubic voxels). Participants will be scanned in a 3.0T Siemens Vida MRI scanner at the Houston Methodist Research Institute outfitted with an MR-compatible LCD display and an MR-compatible 4-response button box. Participants will be screened for metal and other MR-contraindications before entering the scanner.

**RSA.** RSA will be continuously measured during sessions T1 through T5 non-invasively using a Corsense heart rate variability monitor by Elite HRV. RSA will be measured during a 5-minute resting epoch while seated.

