Data analysis will primarily use linear mixed models, incorporating fixed effects for Training Group (Distancing and Reinterpretation), Session (T1-T5), and Trial Type (for analyses involving the reappraisal task; Look Neutral, Look Negative, and Reappraise Negative), and their interactions, as well as a random effect consisting of an intercept for each participant. In each analysis, statistically significant and near-significant intercept variance reflects reliable differences between participants. We will examine additional models that incorporate and estimate random-effects slope variance across participants on the time effect (i.e., Session). Outcome variables will be repeated measures in self-reported negative affect, RSA⁵, and neural activity (Aim 1) and changes in health-relevant behavioral outcomes (e.g., depressive symptoms and grief rumination; Aims 2 and 3). In these analyses, gender, age, baseline depressive symptoms, expectedness of the loss, and current (non-excluded) medication use will be incorporated as covariates. Importantly, given that we anticipate enrolling an approximately equal number of men and women, we also anticipate having sufficient power to conduct exploratory analyses on the effect of gender (and age) on the hypothesized effects (all Aims). Further, Aim 3 will be investigated using multilevel mediation modeling^{6,7} involving training group assignment as the higher-level predictor (X); self-reported negative affect, RSA data, and neural activity as potential individual-level mediators (M); and health-relevant behavior (i.e., depressive symptoms and grief rumination) as individual-level outcome variables (Y). Note that this will model mediation as a time-dependent and experimental process, both of which help

to rule out alternative explanations. Other exploratory model paths will also be tested. Appropriate covariates indicated above will be incorporated in all mediation models.

Data and Safety Monitoring Plan:

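### Every session shows a participant new pictures, but the model has no picture effect, so avoidable noise stays in Group × Session for negative-image ratings

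*Protocol*

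**What the plan says.** **Protocol, Methods, Reappraisal Intervention Procedure.** On image use: "All images at every session will be unique, presented in a randomized order, and counterbalanced across sessions and negative trial types". On numbers: "One hundred and eighty total negative and 90 total neutral images are used in the task, with 18 trials per trial type per session". Negative affect is rated from 1 to 4 after each picture. Neutral pictures appear only under the LOOK cue; negative pictures appear under LOOK and DECREASE.

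**SAP, Data Analysis, All Outcomes.** The model is described as "incorporating fixed effects for Training Group (Distancing and Reinterpretation), Session (T1-T5), and Trial Type", with their interactions, and "a random effect consisting of an intercept for each participant". Additional models add a participant slope on Session. The covariates all describe the participant: "gender, age, baseline depressive symptoms, expectedness of the loss, and current (non-excluded) medication use will be incorporated as covariates". Neither document mentions an image or image-set term, or says whether the model takes single-trial ratings or cell means.

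**SAP, Introduction and Power Analyses.** Task-based negative affect is one of the primary mechanism measures. Power is planned at d=.70 with 36 completers per cell.

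**The concern.** A participant's change from T1 to T5 in one trial type compares the mean of 18 pictures with the mean of 18 others. If some pictures are more upsetting than others, part of that change reflects the pictures drawn and not the training. Rotating pictures over participants keeps this from favouring a session or an arm on average. It does not take the picture variance out of each person's change, and a model without an image term counts that variance as error.

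What is at stake is precision in the Aim 1 comparison of the two trainings on negative affect. The picture shown on each trial is set by the design, so the loss can be largely avoided without collecting anything new.

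**Working it through.** **1. Do T1 and T5 share pictures?** Negative: 18 trials × 2 trial types × 5 sessions = 180. Neutral: 18 × 5 = 90. Both match the Protocol's totals, so no picture repeats for a participant.

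**2. The plan's power figure.** Two-sample t-test (noncentral t), d=.70, 36 per cell, alpha .05: 83.4% two-sided and 90.3% one-sided. The stated 90% reproduces one-sided only, and the SAP does not state sidedness. That is a separate matter; the two-sided figure is the baseline below.

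**3. Picture share of the change variance, one negative trial type.** The documents give no SDs, so these are assumptions: between-picture SD s_i, within-picture trial SD 0.70, and SD s_c of true person-to-person change.

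Share = (2s_i²/18) / (s_c² + 2s_i²/18 + 2×0.70²/18)

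The trial term is 2×0.49/18 = 0.0544. For s_i = 0.30 and s_c = 0.40, the share is 0.0100/(0.1600 + 0.0100 + 0.0544) = 4.5%. If the picture variance is fully removed, d becomes 0.70/√(1 − share).

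| s_i | s_c | Share | d after removal | Two-sided power |
|---|---|---|---|---|
| 0.20 | 0.40 | 2.0% | 0.707 | 84.1% |
| 0.30 | 0.60 | 2.4% | 0.708 | 84.2% |
| 0.30 | 0.40 | 4.5% | 0.716 | 85.0% |
| 0.30 | 0.25 | 7.9% | 0.729 | 86% |
| 0.60 | 0.25 | 25.5% | 0.811 | 92.4% |

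The last row pairs a large picture SD for a 1–4 scale with the smallest change SD considered.

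**4. Can the noise be recovered?** Every participant sees all 180 negative pictures, so picture effects are well estimated when all five sessions and both negative trial types are fitted together. A generalized-least-squares calculation with ten randomly rotated lists of 18 pictures, 36 per arm and known variances, gives a cut in the Group × Session (T5 − T1) variance of about 1% to 4% at picture SD 0.2–0.3 with s_c = 0.40. In the extreme corner the cut is about a quarter. Most of the share in step 3 is therefore recoverable.

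**5. Fixed image-set factor instead.** This was simulated on cell-mean changes with ten lists, 36 per arm, trial SD 0.70 and a between-session person SD of 0.30 per occasion (change SD 0.30×√2 = 0.42).

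- Lists assigned at random, picture SD 0.3: power falls from 0.827 to 0.793.
- List order balanced within arm: power goes from 0.844 to 0.850 at picture SD 0.3, and from 0.857 to 0.879 at 0.5.
- In the balanced case at picture SD 0.5, the model without list terms reports a mean SE of 0.120 against a true SD of 0.114, with type I error 0.037.

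**6. Look Neutral versus Look Negative.** Here pictures are nested in the contrast. Take picture SD 0.30, trial SD 0.70, 72 completers and 72 × 90 = 6,480 ratings per trial type, and consider the picture and trial components only. With an image effect, SE = √(0.09/180 + 0.09/90 + 2×0.49/6480) = 0.041. With picture variance pooled into the residual, SE = √(2×0.58/6480) = 0.013.

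**The case against.** The strongest reply is that the size is assumed throughout. Negative pictures that share grief and loss themes may differ little, and sets matched on average negativity would lower the variance further; the documents do not say whether they are matched. The calculation is also a two-sample test on T5 − T1, not the planned five-session mixed model. All of this stands. It is why the low end is the one to quote and 92% is only a corner.

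A reader might infer that the stated power is too low because of pictures. The documents do not support that. The SAP takes d=.70 from earlier longitudinal reappraisal training data, and that effect size may already include picture noise.

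A reader might also infer bias, or picture differences confounded with Session. That would follow if everyone saw the same set at a given session, but the Protocol says that images are counterbalanced across sessions. Nor is false-positive risk raised for Group × Session: in the simulations, type I error without an image term was close to 0.05 with random lists and below it with balanced lists.

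Finally, it would be too broad to say that an image term sharpens every Session and Trial Type contrast. For Look Neutral versus Look Negative it widens the standard error (step 6), because those conditions never share a picture.

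**Conclusion.** The point holds as a matter of efficiency, limited to Group × Session for negative-image affect ratings. The model leaves out a known source of variance, and the design allows most of it to be recovered. With a picture SD of 0.2–0.3 and a true-change SD of 0.40, the share is about 2% to 5%, and two-sided power moves from 83.4% to about 84%–85%. A smaller change SD of 0.25 gives about 8% and 86% at picture SD 0.30; the 25% share needs picture SD 0.60 as well. All of these rest on SDs that the documents do not supply, and the gain is probably modest. No stated figure is contradicted, and no bias is shown.

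**What to change.** In the SAP, state that negative affect is analysed from single-trial ratings, over all sessions, with a crossed random intercept for image (180 negative, 90 neutral) alongside the participant effects. Put the participant slope on Session in this same model and not only in the additional ones. Otherwise, trial-level data with a participant intercept alone would treat person-to-person differences in change as trial noise.

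Do not use a fixed image-set factor in its place, since it can lower power unless set order is balanced within each arm. State how image sets are assigned to participants.

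The cost is SAP wording, keeping the image identity with each rating, and longer model fitting. The Look Neutral versus Look Negative standard error will be wider. That is the more honest figure if the result is meant to extend beyond these particular pictures, and the SAP should say to expect it.

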Statistical Analysis Plan

Study Title: Neural Mechanisms of Enhancing Emotion Regulation in Bereaved Spouses

ClinicalTrial.gov Identifier: NCT04822194

Sponsor: The National Institute on Aging

Intervention: Cognitive Emotion Regulation Training

Protocol Number: 1

Phase: Phase 1

Statistical Analysis Plan Version: 1.0

May 21, 2025

Principal Investigator: [name]

Rice University

[name]

[name]

United States of America

Statistical Analysis Plan

Introduction:

The objective of this research study is to examine the efficacy and behavioral and neural mechanisms of a cognitive emotion regulation training intervention in bereaved spouses. The primary endpoints are the assessments of the psychological, psychophysiological, and neural mechanisms mediating behavior change as a function of the cognitive emotion regulation intervention. Psychological mechanisms will be assessed by emotion regulation task-based self-reported negative affect. Psychophysiological mechanisms will be investigated by analysis of respiratory sinus arrhythmia data, a measure of heart rate variability reflecting adaptive cardiac vagal tone. Neural mechanisms will be assessed via analysis of fMRI data. The secondary endpoint is testing the efficacy of the intervention via assessment of psychological outcomes (i.e., the behavior change, as represented in changes in depressive symptoms, stress, and grief rumination).

Objectives:

This study represents a Phase I, Stage I clinical trial. The project builds upon promising preliminary work to investigate the effectiveness and underlying neurobiological mechanisms of a novel, five-session cognitive reappraisal intervention in bereaved spouses. The study aims to mechanistically relate changes in psychological, psychophysiological, and neural function during a novel emotion regulation intervention never before implemented in this stressed, high risk group. The goal is to inform future interventions that can reduce negative psychological outcomes in bereaved spouses.

Specific Aims:

- (1) To determine if a relatively brief, focused intervention in reappraisal-by-distancing in bereaved spouses engages the targeted mechanisms. Hypotheses: Distancing training is expected to result in longitudinal reductions in self-reported negative affect, increases in RSA, and changes in neural activity in a priori ROI's above (i.e., reductions in amygdala activity, increases in DLPFC activity) that are greater than those for reinterpretation training.
- (2) To examine the impact of changes in the targeted mechanisms in changing health-relevant behavior. Hypotheses: Across time and participants, reductions in self-reported negative affect, increases in RSA, and changes in neural activity are expected to lead to reductions in depressive symptoms and grief rumination.
- (3) As an exploratory aim, to mechanistically relate intervention effects to behavior change as a function of changes in the targeted processes. Crucially, this aim will also include assessment of interactions with age and gender of the bereaved spouse and initial depression and grief severity.

Hypotheses: Distancing training will lead to reductions in grief rumination and depression that are mediated by changes in the targeted neurobiological and behavioral mechanisms.

Sample Size::

84 bereaved participants will be recruited (i.e., N=42 per each intervention cell) and randomly assigned to receive either Distancing Training or Reinterpretation Training.

Power Analyses:

Outcome: Self-reported negative affect

Sufficient power to assess self-reported negative affect outcomes will be achieved by recruiting 42 participants per training cell. This sample size estimate is based upon a power analysis using an approximate effect size ($d=.70$) previously reported for within and between-subjects behavioral analyses of longitudinal reappraisal training data¹. Power analyses using this approximate effect size indicate over 95% power ($\alpha=.05$) to detect within-group effects and 90% power ($\alpha=.05$) to detect between-group effects should be achieved with 36 participants per cell. Assuming all-cause attrition of 15% (which reflects a liberal upper bound given past participant attrition rates of approximately 10%), the proposed sample size should provide sufficient power to assess this outcome. Post-attrition, we expect to have analyzable complete data for approximately 36 participants per cell.

Outcome: Respiratory sinus arrhythmia (RSA)

Sufficient power to assess respiratory sinus arrhythmia outcomes will be achieved by recruiting 42 participants per training cell. This sample size estimate is based upon a power analysis using an approximate effect size ($d=.70$) previously obtained for within and between-subjects analyses of RSA data². Power analyses using this approximate effect size indicate over 95% power ($\alpha=.05$) to detect within-group effects and 90% power ($\alpha=.05$) to detect between-group effects should be achieved with 36 participants per cell. Assuming all-cause attrition of 15% (which reflects a liberal upper bound given past participation attrition rates of approximately 10%), the proposed sample size should provide sufficient power to assess this outcome. Post- attrition, we expect to have analyzable complete data for approximately 36 participants per cell.

Outcome: Neural activity (fMRI)

Sufficient power to assess neural activity outcomes will be achieved by recruiting 42 participants per training cell. This sample size estimate is based upon a power analysis using a within-subject fMRI effect size estimate for right amygdala affective reactivity from a recent large-scale meta-analysis of fMRI effect sizes using Human Connectome Project data³ of approximately $d=.70$. This effect size estimate is also appropriate for between-subjects neural effects⁴. Power analyses using this approximate effect size indicate over 95% power ($\alpha=.05$) to detect within-group

effects and 90% power ($\alpha=0.05$) to detect between-group effects should be achieved with 36 participants per cell. Assuming all-cause attrition of 15% (which reflects a liberal upper bound given past participation attrition rates of approximately 10%), the proposed sample size should provide sufficient power to assess this outcome. Importantly, this sample size will also account for any participant data loss due to excessive scanner motion (despite mitigation efforts to avoid this), task non-response in the scanner, and poor signal-to-noise in MR signal, in addition to participants dropping out of the study. Each of these classes of participant attrition is expected to be rare. Thus, post-attrition from all causes, we expect to have analyzable complete data for approximately 36 participants per cell.

Outcome: Depressive symptoms, grief rumination, perceived stress, and reappraisal usage frequency.

Sufficient power to assess questionnaire outcomes (i.e., depressive symptoms, grief rumination, perceived stress, and reappraisal usage frequency) will be achieved by recruiting 42 participants per training cell. This sample size estimate is based upon a power analysis using an approximate effect size ($d=.70$) previously reported for within and between-subjects analyses of questionnaire reports measuring these variables (e.g., depressive symptoms²; perceived stress¹). Power analyses using this approximate effect size indicate over 95% power ($\alpha=.05$) to detect within-group effects and 90% power ($\alpha=0.05$) to detect between-group effects should be achieved with 36 participants per cell. Assuming all-cause attrition of 15% (which reflects a liberal upper bound given past participant attrition rates of approximately 10%), the proposed sample size should provide sufficient power to assess this outcome. Post-attrition, we expect to have analyzable complete data for approximately 36 participants per cell.

Definitions of Populations to be Analyzed:

Conditions or Focus of Study

- Bereavement
- Emotions
- Emotion Regulation
- Psychophysiology
- Social Affective Neuroscience

Eligibility Criteria

Inclusion Criteria:

- Recent bereavement of loved one (i.e. loss of romantic partner within the past 5-7 months)
- At least 18 years of age, with no maximum age, provided all other inclusion and exclusion criteria are met.
- Minimum score of 25 on the Inventory for Complicated Grief

- Must be able to speak, read, and write in English
- Must be eligible to safely complete MRI scanning

Exclusion Criteria:

- Death of a second close family member/friend in the past year
- If they are currently receiving psychotherapy
- If they have obstructive pulmonary and/or heart disease, diabetes, liver failure, or kidney failure
- If they have a significant visual, auditory, or cognitive impairment that compromises their ability to understand and complete the task
- If they've gotten divorced within the past year
- Prior participation in similar emotion regulation training protocol in [name] lab
- If they have any contraindication to MRI scanning (i.e. pregnancy, presence of any non-removable metal on or in the body, implanted medical devices, tattoos, medication patches, orthodontic braces or permanent retainers, hearing aids, and history of claustrophobia or breathing disorders)

Data Analysis:

All Outcomes

Data analysis will primarily use linear mixed models, incorporating fixed effects for Training Group (Distancing and Reinterpretation), Session (T1-T5), and Trial Type (for analyses involving the reappraisal task; Look Neutral, Look Negative, and Reappraise Negative), and their interactions, as well as a random effect consisting of an intercept for each participant. In each analysis, statistically significant and near-significant intercept variance reflects reliable differences between participants. We will examine additional models that incorporate and estimate random-effects slope variance across participants on the time effect (i.e., Session). Outcome variables will be repeated measures in self-reported negative affect, RSA⁵, and neural activity (Aim 1) and changes in health-relevant behavioral outcomes (e.g., depressive symptoms and grief rumination; Aims 2 and 3). In these analyses, gender, age, baseline depressive symptoms, expectedness of the loss, and current (non-excluded) medication use will be incorporated as covariates. Importantly, given that we anticipate enrolling an approximately equal number of men and women, we also anticipate having sufficient power to conduct exploratory analyses on the effect of gender (and age) on the hypothesized effects (all Aims). Further, Aim 3 will be investigated using multilevel mediation modeling^{6,7} involving training group assignment as the higher-level predictor (X); self-reported negative affect, RSA data, and neural activity as potential individual-level mediators (M); and health-relevant behavior (i.e., depressive symptoms and grief rumination) as individual-level outcome variables (Y). Note that this will model mediation as a time-dependent and experimental process, both of which help

to rule out alternative explanations. Other exploratory model paths will also be tested. Appropriate covariates indicated above will be incorporated in all mediation models.

Data and Safety Monitoring Plan:

The monitoring for this project will include the Contact PI monitoring of participant safety, adverse event (AE) reporting in compliance with IRB, NIH, and FDA guidelines, and participation in the Continuing Review process with the IRB. The outcomes of IRB reviews are conveyed to the Contact PI via the administrative support staff in the Rice University Office of Sponsored Projects and Research Compliance (SPARC). Given the non-invasive, minimal risk nature of the proposed research, we anticipate that the types of Adverse Events that may occur, if any, will focus on possible distress associated with self-report of grief symptoms or with viewing of grief-related images during the psychological task. The study includes procedures to minimize these risks. All procedures and questionnaires used in this study have been widely and safely used. The Contact PI will assign all research participants a subject identification number for identification purposes. The master list of identifying information (e.g. name, address) will be maintained separately from the other individual-and area-level data, in a firewall and password-protected, encrypted file, on a Rice University institutional server. All data will be coded by number, and numbered codes will be disassociated from subject names and other identifying information. All research staff members are required to respect the confidentiality of participants and to complete rigorous data confidentiality and security training per procedures required by the Rice University IRB.

References

1. Berking, M., D. Ebert, P. Cuijpers, and S.G. Hofmann, Emotion regulation skills training enhances the efficacy of inpatient cognitive behavioral therapy for major depressive disorder: a randomized controlled trial. *Psychother Psychosom*, 2013. **82**(4): p. 234-45.
2. Denny, B.T. and K.N. Ochsner, *Minding the emotional thermostat: Integrating social cognitive and affective neuroscience evidence to form a model of the cognitive control of emotion*, in *Neurobiology of Personality Disorders*, C. Schmahl, K.L. Phan, and R.O. Friedel, Editors. 2018, Oxford University Press: New York. p. 95-109.
3. Denny, B.T., J. Fan, S. Fels, H. Galitzer, D. Schiller, and H.W. Koenigsberg, Sensitization of the Neural Salience Network to Repeated Emotional Stimuli Following Initial Habituation in Patients With Borderline Personality Disorder. *Am J Psychiatry*, 2018. **175**(7): p. 657-664. PMC6032521.

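### The efficacy endpoint is worded as the effect of training, but both arms are trained, so the design identifies only distancing versus reinterpretation

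*SAP*

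**What the plan says.** - **Objective.** The protocol (Objectives) sets out to "examine the efficacy and behavioral and neural mechanisms of a cognitive emotion regulation training intervention". The SAP Introduction repeats this aim. Neither adds a comparator.
- **Endpoint.** SAP Introduction: "The secondary endpoint is testing the efficacy of the intervention via assessment of psychological outcomes". The outcomes it then lists are changes in depressive symptoms, stress and grief rumination.
- **Arms.** Protocol, Design: participants are "randomly assigned to receive training in either distancing or reinterpretation". Neither document describes an untrained, wait-list or attention-control arm.
- **Hypotheses (SAP, Specific Aims).** Aim 1 is explicitly between-arm, but covers only negative affect, RSA and neural activity. Aim 2 relates change in those mechanisms to change in depression and grief rumination, over all participants and time points. The Aim 3 hypothesis begins "Distancing training will lead to reductions in grief rumination and depression" and goes on to say that these reductions are mediated by the mechanisms.
- **Power (SAP, Power Analyses, questionnaire outcomes).** With d = .70 and 36 per cell, the SAP cites over 95% power "to detect within-group effects" and 90% power for between-group effects.
- **Model (SAP, Data Analysis).** Linear mixed models with Training Group, Session (T1-T5) and their interactions. The text does not say which term tests the secondary endpoint.
- **Entry and timing.** Loss of a partner 5-7 months earlier, and "Minimum score of 25 on the Inventory for Complicated Grief" (SAP, Eligibility Criteria). CES-D and UGRS are taken at T1, T5 and one and two months after the intervention; PSS is taken at every session and both follow-ups (protocol, Self-report Questionnaires).

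**The concern.** An endpoint phrased as the efficacy of training asks what would have happened without training. Randomising between two forms of training does not answer that. The quantity the design does identify, the difference between the two tactics, is not written down as a hypothesis for any of the three efficacy scales.

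Three things other than training could lower scores in both arms:

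- natural recovery, mainly by the one- and two-month follow-ups;
- regression to the mean after selection on a high grief score, to the extent that CES-D, UGRS and PSS correlate with the screening inventory;
- repeated completion of the same questionnaires.

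The documents do not say how these would be separated from training. None of the listed covariates (gender, age, baseline depressive symptoms, expectedness of the loss, medication) stands in for an untrained course. At stake is the conclusion on efficacy. A Session effect or a within-arm fall could be read as showing that training works, and more participants would make that misreading more likely.

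**Working it through.** **1. The plan's own power figures.** Inputs from the SAP (Power Analyses): d = .70, alpha .05, 42 recruited per cell, 15% attrition. Sidedness is not stated.

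- Analysable n: 42 x 0.85 = 35.7, about 36. Agrees.
- Within-group: paired t-test, df = n - 1 = 35, noncentrality d x sqrt(n) = 0.70 x 6 = 4.2. Power is 98.3% two-sided (99.3% one-sided), in line with over 95%.
- Between-group: two-sample t-test, df = 2n - 2 = 70, noncentrality d x sqrt(n/2) = 0.70 x sqrt(18) = 2.97. Power is 90.3% one-sided and 83.4% two-sided. The stated 90% is reproduced only one-sided.

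**2. What a within-arm or pooled test would show if training did nothing.** Suppose the training effect is zero in both arms and scores fall for other reasons by d, in standard deviations of the change score. The documents give no value, so d = .2, .3 and .5 are assumptions. The test is a two-sided paired t at .05, with noncentrality d x sqrt(n).

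| Non-training change d | Noncentrality, n = 36 | One arm significant | Noncentrality, n = 72 | Pooled significant |
|---|---|---|---|---|
| .2 | 1.2 | 21.5% | 1.70 | 38.8% |
| .3 | 1.8 | 41.7% | 2.55 | 70.9% |
| .5 | 3.0 | 83.1% | 4.24 | 98.7% |

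The paired test is behaving correctly: the change is real. The error arises only if the change is credited to training.

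**3. The between-arm test under the same assumption.** The arms are randomised, so non-training change is expected to be equal in both and cancels in the difference. The noncentrality is 0 and the rejection rate stays at 5% for every d above.

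**4. Length of the window.** Five sessions, 1-3 days apart, give four intervals: T1 to T5 spans 4 to 12 days. Natural recovery has little time to act there and more by the follow-ups. Regression to the mean and retesting need no long interval.

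**The case against.** The case on the other side is substantial, and several stronger readings that a reader might reach fail against it.

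- *The SAP will declare a within-arm fall to be efficacy.* No sentence says so. Within-group power is standard text repeated for every outcome, always next to between-group power, and the Group x Session interaction is already in the model.
- *The SAP defines efficacy as pre-post change.* It does not. The parenthesis in the Introduction explains which psychological outcomes are meant.
- *Aim 3 credits reductions to distancing with no comparator.* Only the hypothesis wording lacks one. The mediation model in Data Analysis uses training group assignment as the predictor, which is the randomised contrast, and the aim is labelled exploratory.
- *Non-training change is certain and of known size.* The documents give no figure, the screening inventory is not one of the outcome scales, and T1 to T5 is short.
- *The trial needs an untrained arm.* An active comparator is a legitimate choice in a Phase I, Stage I study whose primary endpoints are mechanisms and which aims to inform later interventions.

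All of this stands, and it narrows the point. It does not supply what is missing: an endpoint that the design can identify and a named test for it. The Look versus Reappraise trial contrast gives some within-person control for task affect and fMRI, but none for the questionnaires.

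**Conclusion.** The point holds as a mismatch between the stated endpoint and the design. The efficacy of training as such is not identified; the efficacy of distancing relative to reinterpretation is, and the randomised Group x Time contrast tests it validly. The risk of misreading is an inference from three features taken together: efficacy stated without a comparator, within-group power cited for the same scales, and no between-arm hypothesis or named test for them.

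Its possible size is 22% to 83% significant results per arm and 39% to 99% pooled, against 5% for the between-arm test. This rests on an assumed non-training change of d = .2 to .5, a zero training effect, and 36 analysable participants per arm. The figures illustrate the exposure; they do not forecast what this trial will find. The correction is worth making because it costs little and settles in advance what the trial may conclude.

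**What to change.** 1. In the SAP Introduction, and to match in the protocol Objectives, restate the efficacy endpoint as the comparative efficacy of distancing versus reinterpretation. Changing only the SAP would leave the two documents in conflict.
2. In SAP Data Analysis, name its test: the Group x Time contrast on CES-D, UGRS and PSS, from T1 to T5 and from T1 to the one- and two-month follow-ups. Define Time for these scales, because Session as written stops at T5.
3. State that within-arm and pooled pre-post changes on these scales are descriptive and not evidence of efficacy.
4. In SAP Power Analyses (questionnaire outcomes), rest the efficacy endpoint on between-group power only and state whether the test is one- or two-sided.

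The cost is wording in both documents, with no new participants, data or procedures. The claim becomes narrower: comparative, not absolute. Two consequences should be accepted openly. A finding of no difference between the arms could mean that both tactics work or that neither does. Power also falls quickly if the tactics differ by less than planned: with 36 per arm, a true difference of d = .2, .3 or .5 gives 13%, 24% or 55% power two-sided.
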